## 12.0 Data Management

### Sample size, Statistical Power and Analysis

Sample size justification. As the study is designed to demonstrate feasibility, sample size was determined based on pragmatic considerations, rather than formal power analysis. The study plans to enroll 60 PLWH randomized to CPT-L or Lifesteps. This sample size is adequate to assess feasibility outcomes (enrollment, attrition, retention, adherence to protocol and fidelity). The sample size recruited during our recruitment period (18 months) will allow the team to specifically justify that we can approach a reasonable sample for a larger RCT in an expanded recruitment period. Further, with a target retention rate of ≥90%, an enrolled sample of 60 participants produces a 95% confidence interval from 82% to 98% and an adherence rate of 80% will produce a 95% confidence interval between 70% and 90%. The study will produce both within and between treatment group estimates of visit attendance (yes/no), ART adherence (85% of doses taken), and proportion of detectable viral load (yes/no). Further, if mean HIV Symptom Severity, CD4 cell counts, PCL and CAPS-5 scores will be assessed post-intervention and a sample of 30 participants in each group will provide adequate power to determine estimated a confidence interval with a difference of ½ a standard deviation (0.51 SD) of the between group mean estimate. If the difference in proportion of participants with detectable viral load is 10% in the CPT group and 20% in the SOC Lifesteps group at the close of treatment (10% difference), the sample of 30 participants in each study group will provide an 18% confidence interval on either side of the estimated difference.

Data Analysis Aim 1. All therapy sessions and exit interviews will be audio-recorded and analyzed using NVivo12 software by PI [name] for unique and essential elements to improve the protocol (or CPT intervention). Qualitative data analysis is inductive, iterative, and eclectic. Qualitative content analysis, specifically latent and manifest content analysis, will be used to identify and describe major themes and sub-themes that emerge. This is a dynamic type of analysis oriented toward recognizing, coding and categorizing patterns from text data. Manifest content analysis involves the visible, obvious components of what the transcript says; latent content analysis involves an interpretation of the underlying meaning of the text. Methods are utilized to explore participants' unique perspectives via identification of themes/patterns that naturally emerge from the data and systematic classification of these themes. *[[In qualitative analyses, independent coders will immerse together with their analyses to confirm themes and resolve any divergent analyses through a reconciliation and refinement process.]]* Co-I [name] has utilized this qualitative approach in 8 federally funded studies, where she has published and presented peer-reviewed findings utilizing qualitative data. PI [name] will review emerging themes with the study team, CAB members, stakeholder, and topical experts to incorporate data from qualitative interviews into each step of the refinement process. Consultants [name] and [name] will ensure fidelity to manual for any suggested changes to CPT-L. Data collected will provide the pathway to improve the protocol and ensure feasibility and acceptability. Contingency Plan. Completion of Aim 1 will allow refinements of the integrated protocol of CPT-L for Aim 2. PI [name] has assembled a team with extensive expertise in recruiting high-risk and difficult to engage participants in both PTSD and PLWH (Co-Is [name], [name], [name]; Consultant [name]) and in feasibility testing for clinical interventions (Consultant [name], [name], Co-I [name]). Low acceptability in Aim 1 will prompt meetings with the CAB to make modifications before implementing Aim 2. Any unanticipated challenges to feasibility will be addressed by the qualitative analyses and the approach will be refined. Exit interviews will provide suggestions to improve the protocol. Data will be examined to find whether specific factors explain differential effects among participants.

Data Analysis Aim 2. Descriptive analyses will characterize the entire sample and two conditions as appropriate using measures of central tendency or frequency distributions and proportions. Feasibility will be determined by patient willingness to be screened, proportion of participants meeting PTSD criteria, and flow of participants through the study. Feasibility of assessments will be examined through self-report and medical record abstraction. While CPT has been evaluated in other populations, acceptability within PLWH is important for feasibility data. Intervention feasibility will be monitored through randomization, session attendance and quality assurance data collection on intervention fidelity and supervision. Exit interviews will be analyzed using the same techniques for qualitative analyses described for Aim 1. Study feasibility will be determined by ability to adequately randomize and retain study participants throughout study intervention and follow-up, determined through ability to successfully randomize 4+ patients per month and retain 90% of randomized patients throughout the study. In addition to retention, a low rate of missing primary outcome data ( $\leq 10\%$  missing) will demonstrate ability to integrate the intervention with standard clinical care components and medical health records. Protocol adherence will be monitored weekly and reported as the proportion of weekly PCL checklists completed, and distribution of clinician rated treatment engagement and cooperation levels. Acceptable protocol adherence will be determined by completion of  $\geq 80\%$  of assigned weekly PCL checklists across participants.

In addition to feasibility, efficacy and adherence outcomes will aid in development of the subsequent R01. Parameter and variability estimates of efficacy outcomes will be derived from appropriate statistical models. Specifically, HIV symptom distress (physical and mental), CD4 cell counts, viral load, clinic attendance and ART adherence will be measured at pre- and post-intervention and 3-month follow-up. Proportion of participants with Clinic attendance (yes/no), ART adherence (yes/no), and detectable viral load at the end of treatment and follow up will be compared between study groups using a modified Poisson regression approach with a robust sandwich variance estimator. Initial analytic models for binary outcomes will include the primary treatment effect, study visit and interaction of study visit and treatment as well as variables used to balance the randomization procedure. Adjusted models will explore the additional baseline covariates significantly associated with outcomes. The proportion successful in each treatment group at each visit, the relative risk of success and associated 95% confidence interval will be reported. We anticipate that treatment will decrease CD4 cell counts and HIV

symptom severity more so in the CPT-L group compared to Lifesteps at the follow up clinic visit. Treatment group differences will be assessed using generalized linear models adjusted for baseline cell counts/symptom scores. Normality of model residuals will be assessed using Q-Q plots and data transformations will be performed as needed. The CAPS-5 and PCL will examine PTSD severity at baseline, post-intervention and 3-month follow-up. The PCL will be assessed weekly during study intervention and follow-up. Rates of change from baseline to post-intervention and follow up will be estimated with generalized linear mixed effects regression models. Linear slope trends over time and associated standard errors will be calculated for each treatment assignment using a single model for all data. Estimated CAPS, PCL, and HIV symptom severity scores and associated standard error estimates will be calculated for each study group at each study visit and effect size estimates (Cohen's  $d$ , partial eta) will be tabulated and reported. As PCL scores are measured weekly, non-linear mixed effects models will be fit to not any cubic or quadratic trends that occur during study treatment and estimates of when treatment efficacy begins to show changes in effect size will be assessed and reported.

Exploratory investigations of substance use/misuse will be collected using the AUDIT and DAST. Changes in the proportion of participants reporting substance use between groups following study treatment and follow-up will be compared using modified Poisson regression models adjusted for baseline use and study treatment. Continuous AUDIT and DAST scores will be assessed in those who report use and compared between groups using generalized linear mixed effects models. Depression will be assessed at the same time points using the PROMIS Emotional Distress-Depression short form. Both raw and prorated T-scores will be assessed at each timepoint and treatment group comparisons will be made using generalized linear mixed effect models, adjusted for baseline PROMIS scores and study visit. Exploratory models will be adjusted variables used to balance the randomization procedure and those correlated with study outcomes. Secondary analysis of additional measures (QOL, HIV Stigma, Intersectional Stigma, ERQ) will be assessed between study groups using appropriate statistical methods. Analyses will be conducted using SAS version 9.4 (SAS Institute, Cary, NC, USA).

Exploratory Investigation into Moderators and Mediators. Baseline measures of sex and gender identity as well as history of viral suppression will be assessed as treatment moderators of feasibility, HIV and PTSD outcomes. Moderation will be assessed utilizing addition of interactions into models described above. Although not specifically powered to detect statistically significant interactions, interaction and stratified effect sizes will be presented. Effect sizes will inform relevant hypothesis for future R01 study development. We hypothesize that changes in PTSD-related avoidant coping following the intervention will mediate the relationship between treatment and HIV outcomes at follow up (CD4 Cell Counts, HIV Symptom Severity, ART adherence). Mediation models will estimate indirect and direct effects as well as the proportion mediated using the PROCESS macro. Bootstrap resamples (1000 resamples) will provide point estimates and confidence intervals of the mediating effect of changes in avoidant coping on the relationship between treatment with CPT-L and HIV related outcomes. Feasibility for the subsequent R01 is needed to demonstrate that data can be successfully collected to analyze proposed efficacy and mechanism testing hypotheses (see Form F for Proposed RCT analyses).

Data Capture and Management. This study will use Research Electronic Data Capture (REDCap) for data capture and management. REDCap is a software toolset and workflow methodology for the electronic collection and management of research and clinical trials data. REDCap provides secure, web-based, flexible applications, including real-time validation rules with automated data type and range checks at the time of data entry. Exports are made available for several statistical packages including SPSS, SAS, SATA, R and Microsoft Excel. The study-specific REDCap database will be designed and developed by MUSC research team. The provision of REDCap is made available through the South Carolina Clinical & Translational Research (SCTR) Institute at MUSC with NIH Grant awards UL1RR029882 and UL1TR000062. The recruitment report will be stored in REDCap but will be separate from the research database. Only IRB approved study personnel will have access to the recruitment report. The study team will lose access to the recruitment project at the conclusion of enrollment. The recruitment REDcap will contain both identifiers and health information in the same project.

Regulatory Binders. The MUSC PI will prepare and maintain an electronic regulatory file to include the IRB-approved protocol, IRB correspondence, approved study advertising, and other required study-related regulatory documents.

Deidentification of the research record, data sharing, and retention. At the end of all study activities and upon study closure, the electronic study record will be stripped of any and all personal identifiers. Deidentified data will be maintained per MUSC Records Retention Policy for a period of 6 years for Federal studies before destruction.

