## 1.0 Objectives / Specific Aims

The specific aims of this protocol are to:

**Aim 1.** (Months 03-12). To theater test and deliver the un-adapted CPT protocol and one session adherence intervention (Lifesteps) with 12 trauma-exposed PLWH presenting for HIV treatment at the MUSC Ryan White Clinic and collect qualitative feedback for modifications to ensure feasible administration and relevant incorporation of HIV-related messages and/or content specific to HIV-related PTSD. Specific activities are to:

- A. Test methods and measurement protocol of the beta version of the research protocol.
- B. Utilize feedback provided through exit interviews, topical experts, and advisory panel discussion to shape any refinement of the integrated CPT and one session adherence protocol.
- C. Incorporate qualitative feedback into the CPT-L manual.

**Aim 2.** (Months 13-30). To assess feasibility of the modified CPT protocol (CPT-L) compared to Lifesteps in 60 PLWH with comorbid PTSD over 3 months (baseline, post intervention, 3 month follow-up) in a pilot RCT to assess key variables for subsequent efficacy testing (attendance, ART adherence, HIV symptom distress, CD4 count, viral load, PTSD symptoms, avoidant coping). Specific feasibility benchmarks are:

- A. Achieve a recruitment rate of 4+ patients per month and retention rate of 80% or higher.
- B. Obtain variability estimates of outcomes (less than 10% missing data) and initial indicators of treatment effects for the following hypotheses in the subsequent efficacy trial:
  - a. Participants who receive the CPT-L protocol will have improved HIV symptom distress, ART adherence, clinic attendance, and viral load at post intervention and 3-month follow up vs. control.
  - b. Participants who receive the CPT-L protocol will report lower PTSD at post intervention and 3-month follow up versus those in the Lifesteps Control.
- C. Assess qualitative feedback from exit interviews for high satisfaction, successful saturation of themes, and action plan development, in conjunction with Advisory Board, to refine the intervention for an R01.

**Exploratory Aims.** 1) We will assess between-group differences in other problems that commonly occur among PLWH and PTSD (substance misuse, depression). 2) Avoidant coping will be examined as a potential mechanism of action for the relationship between CPT-L and improved adherence.

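### The 95% intervals given for 90% retention and 80% adherence are correctly computed Wald intervals, a method that performs poorly at 90% and above with 60 participants; name Wilson or exact limits instead (minor)

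*Combined protocol and SAP*

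**What the plan says.** Section 12.0 (Sample size, Statistical Power and Analysis) rests the sample size on pragmatic grounds and not on a power calculation. It then supports the claim that 60 participants are enough for the feasibility outcomes with two precision figures: "with a target retention rate of ≥90%, an enrolled sample of 60 participants produces a 95% confidence interval from 82% to 98" per cent, and "an adherence rate of 80% will produce a 95% confidence interval between 70% and 90" per cent. It does not say how these intervals were obtained, and no interval method is named elsewhere for retention, attendance or other feasibility proportions.

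Retention benchmarks appear in two other places. Aim 2 in section 1.0 asks for a "retention rate of 80% or higher". The Aim 2 data analysis text in section 12.0 judges feasibility by the ability to "retain 90% of randomized patients throughout the study". The same text says that the whole sample and the two conditions will be described with proportions, among other summaries.

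**The concern.** The printed intervals are symmetric about 90% and 80%. At 90% with 60 participants only six are expected to be lost, so the sampling distribution is skewed, and a symmetric interval puts both limits too high. The problem grows as retention rises above 90%, which is where the trial hopes to be, since the target is stated as at least 90%.

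At stake is the quality of a stated precision figure and of the intervals in the eventual feasibility report. Retention is a headline result of a pilot like this one. Because the printed figures are the only indication of method, an analyst could well carry the same formula into the report and obtain limits that under-cover or exceed 100%.

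**Working it through.** **Inputs.** n = 60 enrolled; retention 90% (54/60); adherence 80% (48/60); two-sided 95%, z = 1.96 (all from section 12.0). Arm size 30 (sections 3.0 and 10.0).

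**Step 1: reproduce the plan's figures.** Wald: p ± z·√(p(1−p)/n).
- Retention: 0.90 ± 1.96·√(0.09/60) = 0.90 ± 0.076, or 82.4% to 97.6%. Printed: 82% to 98%.
- Adherence: 0.80 ± 1.96·√(0.16/60) = 0.80 ± 0.101, or 69.9% to 90.1%. Printed: 70% to 90%.

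A continuity-corrected Wald interval also rounds to the first pair (81.6% to 98.4%), but it gives 69.0% to 91.0% for the second. The plain Wald formula therefore fits both, and the printed figures are correct for it.

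**Step 2: Wilson and exact limits.** Wilson: [p + z²/2n ± z·√(p(1−p)/n + z²/4n²)] / (1 + z²/n). With z² = 3.84, z²/2n = 0.0320 and 1 + z²/n = 1.0640:
- 54/60: (0.9320 ± 0.0824)/1.0640 = 79.9% to 95.3%.
- 48/60: (0.8320 ± 0.1062)/1.0640 = 68.2% to 88.2%.

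Clopper-Pearson limits come from beta quantiles.

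| Count | Wald | Wilson | Clopper-Pearson |
|---|---|---|---|
| 54/60 | 82.4-97.6% | 79.9-95.3% | 79.5-96.2% |
| 48/60 | 69.9-90.1% | 68.2-88.2% | 67.7-89.2% |

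For 54/60, the Wald lower limit is 2.5 to 2.9 points above the other two and the upper limit 1.4 to 2.3 points above. For 48/60, the differences are 1.7 to 2.2 and 0.9 to 1.9 points.

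**Step 3: actual coverage of the nominal 95% Wald interval.** This is the sum of the binomial probabilities of all counts whose interval contains the true p.

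| True p, n = 60 | 0.80 | 0.90 | 0.92 | 0.94 | 0.95 |
|---|---|---|---|---|---|
| Wald coverage | 92.2% | 94.1% | 86.1% | 87.9% | 80.6% |

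Wilson coverage is 94.5% or more at each of these values. The cause can be seen at p = 0.95. If 59 or 60 participants are retained, the Wald lower limit already exceeds 95%, and that happens with probability 60·0.95⁵⁹·0.05 + 0.95⁶⁰ = 0.146 + 0.046 = 0.19. In one arm (n = 30), Wald coverage at p = 0.90 is 80.9%.

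**Step 4: limits outside the possible range.**
- 57/60: 0.95 ± 1.96·√(0.0475/60) = 0.95 ± 0.055, so the upper limit is 100.5% (Wilson: 86.3-98.3%).
- 27/30: 0.90 ± 1.96·√(0.09/30) = 0.90 ± 0.107, giving 79.3% to 100.7% (exact: 73.5-97.9%).
- 60/60: the standard error is zero and the interval collapses to 100-100%.

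**Step 5: position relative to 80%.** At 54/60 the Wilson lower limit is 0.15 point below 80% (79.85%) and the exact limit 0.5 point below. The Jeffreys (80.5%) and mid-P (80.4%) lower limits are just above it. At 55/60 the Wilson (81.9%) and exact (81.6%) limits both exceed 80%.

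**The case against.** The case against acting is substantial. The figures are correct for the method used. They are planning illustrations, and nothing commits the final report to Wald. Coverage at 0.90, the value illustrated, is 94.1%, close to nominal. The sample size was set on pragmatic grounds, so no design quantity depends on these limits. All of this stands, and it keeps the point minor.

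A reader might infer something stronger: that the printed lower limit of 82% shows an observed 90% would rule out retention of 80%, the Aim 2 benchmark, and that a valid interval would reverse this. The documents do not support that reading. They nowhere compare a confidence limit with 80%. Both the 80% and the 90% benchmarks are worded as rates to be reached, and 54/60 meets both whichever interval is used. The contrast is also thin and depends on the method: Wilson and exact limits include 80% by 0.15 and 0.5 point, Jeffreys and mid-P exclude it, and one more retained participant removes the difference between Wald and the Wilson or exact limits. Against the 90% criterion, an observed 90% lies inside every interval, so the method changes nothing.

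What the objection does not answer is the behaviour above 90%. The target is at least 90%, so true rates of 0.92 to 0.95 are within what the trial hopes to see, and there the coverage loss and the impossible limits do not depend on any comparison with 80%. The by-arm example is an extension: the plan gives the retention interval for all 60 only, although it does foresee description by condition.

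**Conclusion.** The point holds as a choice of method, not as an arithmetic error, and is of minor severity. The printed limits are about 1 to 3 points higher than Wilson or exact limits. If the same formula were used in the report, nominal 95% intervals for the whole sample would cover about 81% to 88% of the time at true retention of 0.92 to 0.95, and some upper limits would exceed 100%.

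This rests on two assumptions: that the plain Wald formula was used (inferred from its matching both printed intervals), and that participants' outcomes are independent with a common probability. No benchmark, sample size or decision rule changes.

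The conflict between 80% retention in the Aims and 90% in the analysis section is a separate matter and the more consequential of the two.

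**What to change.** In section 12.0, restate the two precision figures using one named method: Wilson (about 80-95% for 90% retention and 68-88% for 80% adherence) or Clopper-Pearson (about 79-96% and 68-89%). Add a sentence saying that all feasibility proportions, overall and by arm, will be reported with that 95% interval.

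The cost is two replaced figures, one sentence and a software option. The stated lower limits fall by about 2 to 3 points, so the precision claim looks slightly less favourable. Nothing else in the design or analysis needs to change.

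In the same edit, reconcile the retention benchmark between section 1.0 (80%) and section 12.0 (90%), and state that it applies to the observed rate, if that is the intention.

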#### AIMS I and II: Inclusion criteria

The primary selection criteria for participants in both Aims of the study will be that the participants meet ALL of the following criteria:

1. Individuals that are 18 years and older
2. Linked with and/or eligible for treatment at MUSC, Roper Ryan White Clinic or other SC HIV care clinic.
3. Participant meets clinically significant threshold of DSM-V PTSD criteria as determined by a Clinician Administered PTSD Scale for DSM-5 (CAPS-5) clinical interview.
4. No changes in psychotropic medication within 4 weeks of study enrollment.
5. Able to speak, read, and write English.
6. Meet at least one of the following HIV care criteria:
  - a. Diagnosed with HIV in the last 3 months;
  - b. Detectable viral load in the last 12 months;
  - c. Failed to show up for or missed 1 or more HIV care appointments in the past 12 months;
  - d. Last HIV care visit was more than 6 months ago;
  - e. Self-reporting less than 90% ART adherence in the past 4 weeks.
7. A score of at least 10 on the adapted Montreal Cognitive Assessment test without visual elements (MoCA-Blind)

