
**Table 2. Research Instruments**

Assessment	Res.	BL	Post	3 mon*	weekly	Description
Demographics questionnaire	P	x				Data collected from participant after consent
BRICS NINR Social Determinants of Health	P	x				18-items assess financial resource strain, physical activity, social connectivity/isolation, safety, family income.
MOS Social Support Survey	P	x				19-items assessing different types of support (emotional/informational, tangible, affectionate, and positive social interaction

[[Montreal Cognitive Assessment Test (MoCA)]]	P					[[A brief 10-item screening tool developed to detect cognitive impairment that measures 8 cognitive domains, takes 5-10 minutes to administer (Nesdarnine et al., 2005), and has been tested in PLWH (e.g., Janssen et al., 2015; Koski et al., 2011).]] MoCA-Blind (without requiring visual elements) will be conducted prior to consent as part of the pre-eligibility process.
HIV, Trauma, PTSD, and Related Outcomes from Clinical Interview and Self-Report						
ART adherence (self-report)	P	x	x	x		ACTG trial adherence measure self-report of medication within the last 4 days and self-efficacy.
Saberi Method Adherence	P	x			X (week 4 and week 8)	Another method for ART adherence through collecting self-rated adherence (SRA), Pill count based adherence (PCA), and Proportion of days covered (PDC). PCA and PDC will be collected by the participant sending a text photograph of pharmacy refill and remainder of pills to a MUSC approved study cell phone. SRA, PCA, and PDC will be collected at Baseline, Week 4, and Week 8.
HIV Quality of Life (WHOQOL-BREF)	P	x	x	x		A 26-item measure categorized into four domains (i.e., physical health, psychological well-being, social relationships, and environment); measures effects of disease and health interventions on an individual's perception of quality of life and assesses changes in quality of life across treatment.
HIV stigma measure	P	x	x	x		Developed by Berger et al. (2001)  , revised by Bunn et al. (2007)  ; multiple dimensions of stigma
[[Everyday Discrimination Scale]]	P	x	x	x		[[Developed by Williams et al (1997), 10-item self report measure is a common approach to measuring intersectional stigma (Turan et al. 2019) by asking parallel questions related to different identities.]]

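### ART adherence is analysed as yes/no at 85% of doses without baseline adherence in the initial model, although some participants can already meet that rule at entry

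*Combined protocol and SAP*

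**What the plan says.** Section 12.0, Sample size, Statistical Power and Analysis, sets the outcome rule where it promises "within and between treatment group estimates of visit attendance (yes/no), ART adherence (85% of doses taken), and proportion of detectable viral load (yes/no". Data Analysis Aim 2 then takes the "Proportion of participants with Clinic attendance (yes/no), ART adherence (yes/no), and detectable viral load at the end of treatment and follow up" and compares them between arms by modified Poisson regression. It adds: "The proportion successful in each treatment group at each visit, the relative risk of success and associated 95% confidence interval will be reported". The initial binary model holds treatment, visit, their interaction and the variables used to balance the randomisation. Section 10.0 names those variables as viral load and gender. Other baseline covariates enter only in exploratory adjusted models, if significantly associated with the outcome. CD4 count and symptom scores, by contrast, are explicitly adjusted for their baseline values.

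Section 5.0 lists five HIV care criteria under "Meet at least one of the following HIV care criteria". Criterion 6e reads "Self-reporting less than 90% ART adherence in the past 4 weeks".

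Table 2 schedules two adherence methods. The first, at baseline, post-intervention and 3 months, is the "ACTG trial adherence measure self-report of medication within the last 4 days and self-efficacy". For the second, self-rating, pill count and days covered, "SRA, PCA, and PDC will be collected at Baseline, Week 4, and Week 8". The plan does not say which method or look-back window feeds the 85% rule.

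**The concern.** The outcome cut-off lies below the entry cut-off. A person who reports from 85% to just under 90% qualifies as poorly adherent under 6e and is adherent under the outcome rule, with no change. A person who enters by 6a to 6d may be fully adherent from the start. The plan sets no minimum change and does not limit success to those below 85% at baseline.

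Aim 2 wants variability estimates and first indications of effect for the efficacy trial, and ART adherence is a named hypothesis. Two things are at stake. A follow-up success proportion in one arm mixes people who improved with people who never needed to. And reducing a percentage to yes/no, without its baseline value in the model, discards information that the trial collects.

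**Working it through.** **1. The plan's own figures.** All four precision figures in the sample-size paragraph reproduce.
- Retention: 0.90 ± 1.96·√(0.9·0.1/60) = 82.4% to 97.6% (stated 82% to 98%).
- Adherence rate: 0.80 ± 1.96·√(0.8·0.2/60) = 69.9% to 90.1% (stated 70% to 90%).
- Mean difference: 1.96·√(2/30) = 0.506 SD (stated 0.51).
- Detectable viral load: 1.96·√(0.1·0.9/30 + 0.2·0.8/30) = 17.9 points (stated 18).

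None of them uses the 85% rule. By the same method, the half-width for a difference in ART adherence is 1.96·√(2p(1−p)/30): 23 points at p = 0.3, 25 at 0.5 and 20 at 0.8.

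**2. The overlap.** On 28 daily doses, 24/28 = 85.7% and 25/28 = 89.3%. Both satisfy 6e and the 85% rule. On a once-daily 4-day recall the possible values are 0, 25, 50, 75 and 100%, so 85% and 90% both mean 4 of 4. The documents do not state dosing frequency.

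**3. Its size, under assumptions.** The documents give no adherence distribution. Assume true adherence is Beta with mean 0.70 to 0.85 and SD 0.10 to 0.20 (seven combinations), entry if the observed 28-dose value is below 90%, and a second 28-dose sample at follow-up with true adherence unchanged. Results are for 6e entrants only:

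| Quantity | 85% cut-off | 90% cut-off |
|---|---|---|
| Success at baseline | 15-38% | 0% by construction |
| Success at follow-up, no effect | 17-44% | 6-19% |
| Rise within an arm, no effect | about 2-6 points | 6-19 points |

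Of those below 85% at entry, 11-30% cross by chance. Adding a lower mean (0.60, SD 0.20) widens this to 6-30%, and baseline success then starts at 9%. As a cruder check, if reported values were uniform from L to 90%, the overlap is 5/(90−L): 6% for L = 0, 25% for L = 70 and 50% for L = 80.

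**4. The between-arm comparison.** With equal true success rates of 20%, 30% and 50% and 30 per arm, the simulated two-sided error of a Wald test on the log relative risk is 2.6% to 5.3%. Baseline success and chance crossing fall on both arms alike and create no false difference.

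**5. Precision.** Under the same seven distributions, with an illustrative 30% cut in missed doses and 30 per arm, expected z is:

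| Analysis | 28 doses | 4-day recall, once daily |
|---|---|---|
| Yes/no at 85% | 1.3-1.8 | about 1.0-1.1 |
| Yes/no at 90% | 1.0-1.4 | same as 85% |
| Percentage, adjusted for baseline | 2.6-3.7 | 1.2-1.6 |

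On 28 doses, baseline adjustment alone brings the 85% outcome to roughly 1.6-1.9, and the unadjusted percentage gives about 2.0-2.5. Dichotomising and omitting the baseline therefore each cost something.

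**The case against.** The strongest reply is that an outcome threshold need not equal a screening threshold. The trial is a feasibility pilot of pragmatic size, no precision figure rests on the 85% rule, and the analysis compares randomised arms rather than counting responders by change. Someone adherent at both visits shows no improvement. Success is to be reported at each visit, so baseline status could be displayed, and baseline adherence could enter through the exploratory adjusted models.

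Much of this stands. A reader might infer that many participants become successes by noise alone. The documents give no figure for that: the result runs from few to many with the instrument, the window and the distribution, and the share who enter by 6e is unknown. A reader might also infer that within-arm results will show a large spurious improvement. At the 85% cut-off the no-effect rise from baseline is only about 2-6 points. Nor does the overlap bias the treatment comparison.

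Aligning the two cut-offs at 90% is a tempting remedy, but it works against its purpose. It sets baseline success among 6e entrants to zero, so the no-effect rise becomes 6-19 points, and it lowers expected z.

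The reply does not settle two points. Displaying baseline status is possible but not stated, and letting baseline adherence in only if it proves significant is weaker than the adjustment the plan already gives CD4 count and symptom scores.

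**Conclusion.** The concern holds as a matter of interpretation and precision, not of bias. That a participant can meet the 85% rule at entry follows from the text alone. How many do so is not derivable; 15-38% of 6e entrants is conditional on a 28-dose measure and the assumed Beta distributions, and says nothing about entrants by 6a to 6d. A follow-up success proportion therefore cannot be read as improvement unless baseline status is shown beside it.

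The loss of precision is clear on a 28-dose measure (expected z 1.3-1.8 against 2.6-3.7) and modest on the 4-day recall (about 1.0-1.1 against 1.2-1.6). The recall is the only adherence instrument scheduled at both post-intervention and 3 months. These values rest on binomial dose-taking without reporting error and on an illustrative effect that is not in the documents. No main feasibility conclusion depends on this point; it is a cheap improvement to a named planning outcome.

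**What to change.** In section 12.0, in both the sample-size text and Data Analysis Aim 2:

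1. Add, as the lead ART adherence estimate, the between-arm difference in percentage of doses taken, adjusted for its own baseline value. Use the 4-day ACTG percentage at post-intervention and 3 months, and the self-rated and pill-count percentages at weeks 4 and 8. The latter have no 3-month reading, and week 4 falls within the roughly 6-week treatment period, so they cannot replace the ACTG result.
2. Keep the 85% yes/no outcome as secondary, and name baseline adherence as a covariate in its modified Poisson model.
3. Tabulate baseline status by follow-up status in each arm.
4. State which instrument and look-back window feed the 85% rule, and give the reason for its difference from 6e.
5. Leave the outcome cut-off at 85%.

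The cost is wording, since the data are already scheduled for collection. The downsides are that percentage adherence is skewed (the plan already allows transformations for its linear models), that a mean difference is less familiar than a proportion, and that the gain on the 4-day recall is small.
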